4.5 Microbiologically Evaluable Populations

The microbiologically evaluable (ME) population will include subjects in the CE population who have a study-qualifying pre-treatment Baseline urine culture with 1 or 2 uropathogens at $\geq 10^5$ CFU/mL.

Since patient count may differ depending on timepoint, ME populations will be defined by milestone visit (ME-EOT and ME-PTE).

The ME populations consist of subjects in the micro-ITT population and the CE-EOT and CE-PTE populations, respectively who also have:

- A clean-catch urine specimen at the EOT and PTE visits, and
- Interpretable urine culture results at the EOT and PTE visits.

An interpretable post-baseline urine culture is one that has a clearly identified pathogen or one where the baseline pathogen(s) can be excluded (ie, there is no growth of the baseline pathogen), for further details refer to [Pathogen and CE Review Plan: PTK0796-uUTI-17201²](#).

Subjects with an unfavorable microbiological outcome at EOT will be included as microbiological failures in the ME-PTE population, regardless of whether they provide a urine culture at the PTE visit.

At any visit after Screening, a pathogen the same species as the Baseline pathogen with a CFU count of $\geq 1 \times 10^4$ CFU/mL should be considered a persisting pathogen.

At any visit after Screening, any culture with a CFU count of $< 10^4$ CFU/mL should be considered a negative culture.

4.6 Additional Populations

For the purpose of sensitivity analyses described in [Section 7.5.1](#), the following modified micro-ITT populations are defined.

The modified microbiological ITT 1 (micro-m1ITT) population will consist of subjects in the ITT population who have a study-qualifying pre-treatment Baseline urine culture with 1 or 2 uropathogens at $\geq 10^4$ CFU/mL.

The modified microbiological ITT 2 (micro-m2ITT) population will consist of subjects in the ITT population who have a study-qualifying pre-treatment Baseline urine culture with 1 or 2 uropathogens $\geq 10^3$ CFU/mL.

5 OVERALL STATISTICAL CONSIDERATIONS

5.1 General

All analyses will use SAS version 9.4 or higher. Results will be reported by treatment group.

Unless otherwise noted, categorical variables will be summarized using counts and percentages. Percentages will be rounded to one decimal place except for 100%, which will be displayed without any decimal places. In addition, percentages will not be displayed for zero counts.

Continuous variables will be summarized using the number of observations (n), mean, standard deviation (SD), median, minimum and maximum.

5.1.1 Definitions

In [Table 2](#) the general definitions provided are used in the statistical analysis.

Table 2 General Definitions

Variable	Definition
Baseline	Unless otherwise stated, baseline is defined as the value closest to but prior to the initiation of test article administration.
Change from baseline	Change from baseline will be defined as the post-baseline value minus the baseline value (on a subject level). Change from baseline will only be calculated for subjects who have both baseline and at least one post-baseline value for any parameter.
Duration Variables	Duration variables will be calculated using the general formula: Duration (days) = End date - Start date + 1 If applicable, where time is collected: Duration (hh:mm) = End datetime - Start datetime
Calculated Creatinine Clearance (mL / min), Cockcroft-Gault equation	$\frac{(140 - \text{age [yrs]}) * \text{weight [kg]} * Z}{\text{Creatinine [mg/dL]} * 72}$ Z = 0.85 for Female subjects
Body Mass Index (BMI)	$\text{BMI} = \text{Weight (kg)} / \text{Height (m)}^2$

5.1.2 Missing Data and Data Imputation Methods

Missing data will be handled as outlined below

1. Adverse Events and Safety Data:

- All missing and partial dates for AEs will be queried for a value. If no value can be obtained, substitutions will be made as detailed in [Section 8.4](#) (Adverse Events). These

substitutions will be used in calculations; however, the actual value recorded on the eCRF will be used in all listings.

- If the time of the first dose of test article is missing, it will be imputed with time of randomization + 1 minute. If time is missing for other doses it will be imputed with time of previous dose + 12 h.
- An AE is considered treatment emergent if the AE start date and time is on or after the start date and time of the first dose of test article.

If time of the AE is missing and it occurred on the same date as the first dose of test article, the AE will be defined as treatment emergent. If the start date of the AE is partial or missing and it cannot be determined if the AE occurred prior to or after the first dose of test article, the AE should be defined as treatment emergent. [Table 3](#) provides imputation for partial or missing date information. For AE listings, all dates and times will be displayed as reported on the Case Report Forms.

Table 3 Adverse Event Start/Stop Date Imputation

Parameter	Missing	Additional Conditions	Imputation
Start date for AEs	D	M and Y same as M and Y of first dose of test article	Date of first dose of test article
		M and/or Y not same as date of first dose of test article	First day of month
		Y same as Y of first dose of test article	Date of first dose of test article
	D and M	Y prior to Y of first dose of test article but same as Y of screening date	Date of screening date
Stop date for AEs	D, M, Y	None - date completely missing	Date of first dose of test article
		M and Y same as M and Y of last dose of test article	Date of last dose of test article
	D	M and/or Y not same as date of last dose of test article	Use last day of month
		Y same as Y of last dose of test article	Date of last dose of test article
D and M	Y not same as Y of last dose of test article	Use Dec 31	
	D, M, Y	None - date completely missing	No imputation, but assume ongoing

D=day, M=month, Y=year

Note: In all cases, if an estimated start date is after a complete stop date, use the first day of the stop date month. Similarly, if the estimated stop date is before a complete or imputed start date, use the last day of the start day month.

In all cases, if it cannot be determined if the adverse event occurred prior to or after the first dose of test article, the adverse event should be defined as treatment emergent.

- If no value can be obtained for all other times for events and assessments occurring after randomization, the time will not be imputed but will remain missing.
- The severity and causality assessment for AEs cannot be missing. Missing data will be queried for a value. The highest severity and most related causality should be used if query is missing. If query will return missing, then the highest severity and most related causality will be used for the purpose of summaries.
- If the reported value of a clinical laboratory parameter cannot be used in a statistical summary table (eg, a character string is reported for a parameter of the numerical type), a coded value must be appropriately determined and used in the statistical analyses. A

value or lower limit of normal range (eg will be calculated as 99.99% of the value if it is reported as “<” (eg <5 will be converted to $5 \times 0.99 = 4.9995$). The upper normal range of a value will be converted to 100.01% if it is reported as “>” (eg >7 will be converted to $7 \times 1.001 = 7.007$). However, the actual values as reported in the database will be presented in data listings.

- Prior and Concomitant Medication Start Date Imputation will be imputed according to table in [Appendix 4 Concomitant Medication Start Date Imputation](#).

2. Efficacy Data

- Analysis of efficacy data will be based on the available data, unless otherwise stated.
- Missing data for clinical and microbiological outcomes will be denoted “indeterminate” unless otherwise stated.
- Missing microbiological outcomes at EOT will be imputed by last day of test article intake.
- The Overall Clinical Response at PTE and FFU visits are derived based on the “worst case scenario” to accommodate for missing visit assessments and intercurrent events (eg rescue medication at EOT visit). Similar imputations were applied to microbiological response endpoints. Details are described in [Section 7](#).
- UTISA data for bothersome score will be imputed with score of 0 for each question for which severity is answered “Did not have”.
- Missing UTISA responses at baseline will be imputed with Day 1 responses.

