7.1.2.2 Microbiologic Response

Per-pathogen microbiological response will be programmatically determined at the EOT and PTE Visits in the micro-ITT and ME populations (by definition subjects in the ME population cannot have an indeterminate response).

Pathogen microbiological outcome categories are: eradication, persistence, and indeterminate and these are defined in [Table 7](#). Favorable microbiological outcomes include eradication. Unfavorable microbiological outcomes include persistence or indeterminate.

Table 7 Pathogen Microbiological Outcome Categories at EOT and PTE

Category	Criteria	Interpretation
Eradication	Urine specimen shows absence of the original baseline pathogen or the baseline pathogen grew at $<10^4$ CFU/mL at visit.	Favorable
Persistence	Urine culture shows continued presence (defined as $\geq 10^4$ CFU/mL) of the original baseline pathogen(s) at visit.	Unfavorable
Indeterminate	Urine specimen was not available to culture (or the culture result was not interpretable).	Unfavorable

*for PTE visit use Overall Clinical Response at PTE

Per-subject microbiological responses will be based on per-pathogen outcomes. To have an overall per subject favorable microbiologic response, the outcome for each baseline pathogen must be favorable. If the outcome for any baseline pathogen is unfavorable, the subject will be considered to have an unfavorable per-subject microbiologic response. Subjects with an indeterminate response for all baseline pathogens will be considered to have an indeterminate per-subject microbiologic response. Subjects with at least one indeterminate response for a baseline pathogen when all other baseline pathogens have a favorable response will be considered to have an indeterminate per-subject microbiologic response.

Table 8 Per-Subject Microbiologic Response

Condition	Microbiologic Response at Visit	Per-Subject Microbiologic Response at Visit
All per-pathogen microbiological responses at visit	Favorable (Eradication)	Favorable
Any per-pathogen microbiological response at visit	Unfavorable (Persistence)	Unfavorable
All per-pathogen microbiological responses at visit	Indeterminate	Indeterminate
At least one per-pathogen microbiological response at visit when other responses are Favorable (Eradication)	Indeterminate	Indeterminate

[figure not shown]

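### SAP 5.1.2 imputes a missing EOT microbiological outcome by an undefined rule that conflicts with Table 7 and, on one reading, can score eradication from urine taken on drug

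*SAP*

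**What the plan says.** SAP 5.1.2, under Efficacy Data, has three relevant bullets.

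- The default: "Missing data for clinical and microbiological outcomes will be denoted “indeterminate” unless otherwise stated".
- Directly after it: "Missing microbiological outcomes at EOT will be imputed by last day of test article intake".
- Then a worst-case derivation for the overall clinical response, with the remark "Similar imputations were applied to microbiological response endpoints" and a pointer to Section 7 for details.

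Section 7 and related sections say the following.

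- **Table 7 (7.1.2.2)** covers both EOT and PTE. It assigns Indeterminate when "Urine specimen was not available to culture" or the result cannot be interpreted, and makes no exception for an earlier culture. The text above it reads "Unfavorable microbiological outcomes include persistence or indeterminate".
- **Table 9** keeps Indeterminate as a separate EOT input. EOT Indeterminate with PTE Favorable gives Indeterminate overall. Its footnote equates Unfavorable with persistence.
- **7.3.2** tabulates persistence and indeterminate together as unfavorable.
- **5.1.3** bases micro-ITT efficacy on data from the EOT, PTE and FFU visits themselves.
- **4.5** requires a urine specimen at EOT and PTE for the ME populations, but also states: "Subjects with an unfavorable microbiological outcome at EOT will be included as microbiological failures in the ME-PTE population".

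Protocol 12.6.2 expects an indeterminate category for the EOT microbiologic response, and SAP Section 9 declares no changes from the protocol.

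**The concern.** The imputation sentence leaves open which culture stands in for the missing one, whether a Day 3 or Day 5 urine qualifies, and whether imputation happens before or after Table 7 is applied. Two programmers working from this text could score the same woman differently on a listed secondary endpoint.

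The choice matters because the only cultures scheduled between first dose and EOT are on Days 3 and 5 (Protocol 9.2.2 and 9.2.3), both during dosing. Protocol 7.4 cites mean urinary omadacycline on Day 5 of 17 to 30 µg/mL (300 mg) and 30 to 48 µg/mL (450 mg) from the earlier cystitis study, against an *E. coli* MIC90 of 2 µg/mL. Protocol 7.3 describes nitrofurantoin as concentrating well in urine. No growth in such a sample is weak evidence of eradication.

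The primary clinical endpoint takes the opposite approach. Table 5 scores a missed EOT assessment followed by PTE success as Indeterminate.

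**Working it through.** The plan gives no figure to reproduce: neither the number of missing EOT cultures nor the micro-ITT size is stated.

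**Step 1. Possible readings of the sentence.**

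- Narrow: use a culture taken on the last dosing day. That day already lies inside the EOT window (Protocol 9.4), so little changes.
- Broad: carry forward the last on-treatment culture (Day 3 or Day 5).
- A third possibility is that only the date of the outcome is imputed.

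The text does not decide between them. The rest of this check takes the broad reading.

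**Step 2. Table 9 for a woman with no EOT culture.**

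| PTE culture | Overall PTE, EOT Indeterminate (Table 7) | On-drug culture negative, imputed Favorable | On-drug culture positive, imputed Unfavorable |
|---|---|---|---|
| Favorable | Indeterminate | Favorable | Unfavorable |
| Unfavorable | Unfavorable | Unfavorable | Unfavorable |
| Missing | Indeterminate | Indeterminate | Unfavorable |

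The overall PTE result improves in one cell only: EOT culture missing, on-drug culture negative, PTE culture favorable. A woman who never returns can be Favorable at EOT, but stays Indeterminate overall at PTE.

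**Step 3. Size at EOT, micro-ITT.** Let m be the share with no EOT culture, e the eradication rate among those cultured, and q the share of on-drug cultures that are negative. Every missing woman is assumed to have an on-drug culture. All three values are assumptions.

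- Table 7 rule: favorable rate = (1 − m) × e.
- Broad imputation: favorable rate = (1 − m) × e + m × q.
- Difference = m × q, whatever e is.

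| m | m × q at q = 0.70 | m × q at q = 1.00 | Table 7 rate at e = 0.80 | Imputed rate at e = 0.80, q = 0.90 |
|---|---|---|---|---|
| 5% | 3.5 points | 5.0 points | 76.0% | 80.5% |
| 10% | 7.0 points | 10.0 points | 72.0% | 81.0% |
| 15% | 10.5 points | 15.0 points | 68.0% | 81.5% |

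For scale, about 225 subjects over five arms is 45 per arm in ITT. If 30 of them were in micro-ITT (assumed), one woman is 1/30 = 3.3 points, and 5% to 10% missing is 1.5 to 3 women per arm. Women who stop before Day 3 have no on-drug culture, which makes the shift smaller than shown.

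**Step 4. The ME populations.** The CE criteria in 4.4 ask for a clinical assessment, not a urine. A woman assessed at EOT who gives no specimen can therefore be clinically evaluable. The specimen condition in 4.5 then excludes her from ME. If Indeterminate is read as unfavorable, as 7.1.2.2 has it, the later sentence in 4.5 counts her as an ME-PTE failure. The Table 9 footnote points to persistence as the intended meaning.

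**The case against.** The strongest defence is that the sentence follows a default that yields to stated exceptions, so within 5.1.2 it can stand as one. That reconciles the first two bullets. It does not reconcile the sentence with Table 7, or with the worst-case bullet that defers to Section 7, where the visible text contains no such imputation. Some SAP text is redacted, and the Pathogen and CE Review Plan is not public; either could define the source culture. Table 7 is visible, however, and carries no exception.

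It is also fair that on-drug sampling is not peculiar to imputed cases, since a regular EOT urine may be taken on the last dosing day. The microbiological response is meant to support the clinical findings, and SAP 5.1.4 makes all inference nominal. These points limit the weight of the problem; they do not remove the conflict.

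A reader might infer three stronger conclusions, which the documents do not support.

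- *Women who stop and never return become microbiological successes.* This can happen at EOT only, and only on the broad reading. Their overall PTE response stays Indeterminate, which 7.3.2 counts as unfavorable. A positive on-drug culture would be imputed as persistence.
- *Such a woman could also be an ME-PTE failure, giving three conflicting scores.* Having missed both visits, she is Indeterminate under Table 5, so she is outside CE-PTE and hence outside ME-PTE. In micro-ITT, Indeterminate and unfavorable give the same favorable rate.
- *The rule favors the arm with more intolerance.* Protocol 7.4 reports one discontinuation for nausea and/or vomiting among the first 145 subjects (1/145 = 0.7%), reviewed blinded. Those data predate the 450 mg twice-daily arm, so its rate is unknown. Nothing in the documents shows differential stopping.

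**Conclusion.** The point holds as an unresolved contradiction. SAP 5.1.2 imputes a missing EOT microbiological outcome by an undefined method. Table 7, Table 9, 7.3.2 and the worst-case statement in 5.1.2 make the same outcome Indeterminate and not favorable.

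Its reach is the secondary micro-ITT microbiological response at EOT and, where the PTE culture is favorable, the overall response at PTE. ME requires an actual EOT specimen, and the primary endpoint is clinical, so neither gains from the imputation.

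The size, m × q, rests on assumed inputs and on the broad reading. On the narrow reading the effect is small. The contradiction itself depends on none of these assumptions.

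**What to change.** Before unblinding:

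1. Delete the imputation sentence from SAP 5.1.2 so that Table 7 governs: no EOT specimen is Indeterminate and not favorable in micro-ITT.
2. If the last on-treatment culture is of interest, report it as a labelled sensitivity analysis that names the source culture and applies the imputation before Tables 8 and 9.
3. In 4.5, make the ME-PTE failure sentence refer to persistence at EOT instead of an unfavorable outcome, in line with the Table 9 footnote. A clinically evaluable woman without an EOT specimen is then not both excluded from ME and counted as an ME-PTE failure.

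This takes two wording edits and no new data. SAP 3.5 provides for amendments approved before database lock. The downside is a slightly lower EOT favorable rate than carrying forward on-drug cultures would give.

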5.1.3 Visit Windows

For efficacy outcomes, the data collected at the EOT, PTE and FFU visits, regardless of when these occur will be utilized in the analysis of the ITT and micro-ITT populations. The CE and ME populations exclusions due to windowing are outlined in [Sections 4.4](#) and [4.5](#).

For each safety outcome and UTISA data, analyses will utilize assessments occurring during the scheduled visit windows (provided in [Table 4](#)). Thus, if a subject has a visit outside the scheduled visit window, for example, a PTE Visit occurred 20 days after the subject's last day of therapy, the assessment will not be summarized with the PTE Visit but will be considered an unscheduled assessment. If a subject does not have an assessment at a scheduled visit and an unscheduled assessment was taken within the window for the time point (for example, 14 days [\pm 2 days] after the subject's first day of therapy for PTE), these assessments will be summarized in the by time point analyses. If more than one measurement is taken during the visit window, the value taken on the scheduled visit will be utilized or if no scheduled visit was done, the first (earliest) measurement in the visit window will be used. If more than one measurement is taken on the same day, the assessment closest to the start of the dose will be used for on-treatment values and the last measurement on the day will be used for post-treatment values. For worst overall post-baseline analyses, all assessments including those obtained from unscheduled visits will be included.

Table 4 Scheduled Study Visits

Study Visit	Study Day	Notes
Baseline	Day -1 or Day 1	Except where indicated, last measurement prior to the first dose of test article. Screening assessments are to be taken within 24 hours prior to randomization if no test article is taken, the date and time of randomization is used in place of randomization date.
On Treatment (note: analysis visit will be each Study Day)	Day 1- 6	As entered in the eCRF* for these visits
EOT	Day 7	Within 2 days following the last dose of test article
PTE	Day 14	14 ± 2 days after the subject's first dose of test article
Final Follow-up (FU)	Day 30 to 37	30 to 37 days after the start of the first dose of test article

Study Day is calculated relative to the first dose of test article (Day 1); there is no Day 0 – the day prior to the first dose of test article is Day -1. If no test article is taken, study day is calculated relative to the date of randomization. *Days 2, 4, 6 are completed at home.

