 - 1) Since the driver of efficacy is unknown and the mean renal excretion of a 300 mg oral dose is 14.4%, a regimen that maximizes the tolerated dose of omadacycline may provide additional information on the dose necessary for

clinical and microbiologic success in uUTI and allow comparison to the daily dosed omadacycline treatment groups.

- 6) The proposed dosing of 450mg twice daily for 7 days will provide approximately 2x or greater the amount of omadacycline that is excreted into the urine compared to the daily omadacycline treatment groups.
- 7) Blinded review of the first 145 subjects reveals good tolerability. Nausea has occurred in approximately 10% of all subjects with only a single subject (0.7%) reporting vomiting. There has been only one treatment discontinuation due to adverse events of nausea and/or vomiting reported. Therefore, even if all cases of nausea and vomiting were in a single omadacycline treatment group, nausea and vomiting appears lower than observed in PTK0796-UUTI-15103 study.
- 8) Dose-limiting transaminase increases were seen in Phase 1 studies at 600mg IV which is higher than the exposure at 450mg PO twice daily.
- 9) Increases in heart rate following omadacycline are C_{max} associated. C_{max} concentrations with the 450mg PO dose (1077 ng/mL) at steady state are approximately one-half the C_{max} concentration with the 100mg IV dose (2120 ng/mL) suggesting that heart rate increases above 12-17 bpm observed with 100-200mg IV doses in healthy patients is unlikely following 450mg twice daily dosing.

Therefore based on the pharmacokinetic, clinical, and safety data, the 450mg twice daily dose will increase urinary concentration, may provide additional clinical and microbiologic benefit while maintaining the safety profile observed with daily dosing.

In order to minimize the effect of food on exposure and to potentially minimize the impact of nausea and vomiting during the omadacycline loading dose, omadacycline will be dosed twice on Day 1 with each dose administered approximately 2 hours following a light meal. In addition, all even numbered doses will also be administered approximately 2 hours following a light meal. Given the urinary concentrations observed in PTK0796-UUTI-15103 and the expected impact of a light meal, urinary concentrations should remain above the typical omadacycline MIC₉₀ of 2 µg/mL for *E.coli*, the most common uropathogen in uncomplicated cystitis.

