8.5 Vital Signs

Vital signs include blood pressure (BP), heart rate, body temperature, height and body weight.

- Blood pressure and heart rate should be measured within 30 min before, and approximately (\pm 15 minutes) 1 hour after and 3 hours after the completion of the first dose.

The subject's vital signs should be captured after at least 5 minutes (+ 5 minutes) of rest while in a non-standing position (supine or semi-recumbent, head of bed from 0° to 90°). Subsequent vital sign measurements should be captured in the same non-standing position.

Systolic and diastolic BP will be measured using an automated validated device, with an appropriately sized cuff.

Heart rate will be measured using an automated validated device, when available. If not available, heart rate will be measured manually.

Temperature will be obtained using an electronic (rapid reading) device whenever possible.

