12.6 Secondary Endpoint(s)

12.6.1 Safety Endpoint(s)

All safety analyses will utilize the Safety population. Summary tables will be provided for all treatment-emergent adverse events (TEAEs). A TEAE is defined as an AE with a start date and time on or after the first dose of test article. AEs will be coded using the Medical Dictionary for Regulatory Activities (MedDRA) and will be summarized by presenting the number and percentage of subjects having each TEAE for each treatment group by system

organ class (SOC) and preferred term (PT), by SOC, PT and severity, and by SOC, PT and relationship to test article. Additional tabulations will provide summaries by SOC and PT of subjects experiencing SAEs and TEAEs judged to be related to test article.

The following variables will be analyzed descriptively by treatment group in the Safety population:

- Vital signs (systolic and diastolic BP, heart rate, body temperature), including change from Baseline by visit and time point measured
- Clinically notable vital signs (meeting predefined criteria as specified in the SAP) by visit and time point measured
- Laboratory parameters, including change from Baseline by visit
- Clinically notable laboratory parameters (meeting predefined criteria as specified in the SAP) by visit

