8.6 Vital Signs

Vital signs will include blood pressure (diastolic and systolic), heart rate, and body temperature, and will be collected at Screening, Days 1, 3, 5, and EOT, as well as at the PTE. During the Follow-up call/visit vital signs are collected if the subject reports symptoms of potential recurrence and clinic visit is required.

Additionally, height will be collected at the Screening visit, and body weight will be collected at the Screening and EOT visits.

Blood pressure (systolic and diastolic) and heart rate will be summarized by time point and for the minimum and maximum post-baseline values using descriptive statistics, for both the actual values and the change from baseline.

Figures (line graphs) of observed values for heart rate, systolic and diastolic blood pressure over time will also be provided by treatment group.

Post-baseline vital signs will be defined as CN if they meet 1) the criterion value at the given visit, or 2) meet both the criterion value and the change from baseline criterion listed in [Table 11](#). The incidence of CN vital signs will be summarized by time point and treatment group and will be listed and flagged in by-subject listings. An overall post-baseline incidence of CN values for each vital sign parameter, will also be summarized. A separate listing will be provided of subjects with values for a vital sign noted as CN.

Table 11 Criteria for Clinically Notable Vital Signs

Vital Sign Parameter	Flag	Criterion Value	Change from Baseline
Systolic Blood Pressure (mmHg)	High (CH)	≥ 180	Increase of ≥ 20 mmHg
	Low (CL)	≤ 90	Decrease of ≥ 20 mmHg
Diastolic Blood Pressure	High (CH)	≥ 105	Increase of ≥ 15 mmHg

Table 11 Criteria for Clinically Notable Vital Signs

Vital Sign Parameter	Flag	Criterion Value	Change from Baseline
(mmHg)	Low (CL)	≤ 50	Decrease of ≥ 15 mmHg
	High (CH)	≥ 120	Increase of ≥ 15 bpm
Heart Rate (bpm)	High (CH)	≥ 120	Increase of ≥ 15 bpm
	Low (CL)	≤ 50	Decrease of ≥ 15 bpm

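### The SAP's one-value-per-day rule cannot keep both scheduled post-dose Day 1 heart-rate and blood-pressure readings in the by-visit summaries, and the change column of SAP Table 11 never affects a flag

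*SAP*

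**What the plan says.** **Collection.** Protocol 8.5 fixes three Day 1 readings around the first dose: "Blood pressure and heart rate should be measured within 30 min before", and then "1 hour after and 3 hours after the completion of the first dose". The post-dose readings carry a 15-minute tolerance on either side, which note j of the Schedule of Events repeats.

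**Protocol analysis.** Protocol 12.6.1 plans descriptive vital-sign summaries "including change from Baseline by visit and time point measured". It plans clinically notable (CN) vital signs on the same footing.

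**SAP selection rule.** SAP 5.1.3 covers every safety outcome. Where a day has several readings, "the assessment closest to the start of the dose will be used for on-treatment values". Table 4 of that section makes each study day an analysis visit during treatment. For worst post-baseline analyses, 5.1.3 uses all assessments instead.

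**SAP baseline.** Under Table 2 (SAP 5.1.1), "baseline is defined as the value closest to but prior to the initiation of test article administration". The Baseline row of Table 4 likewise points to the last pre-dose measurement and allows it to fall on Day 1.

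**CN rule.** SAP 8.6 calls a post-baseline vital sign CN if "they meet 1) the criterion value at the given visit, or 2) meet both the criterion value and the change from baseline criterion". For high heart rate, Table 11 gives a criterion value of 120 bpm or more and a rise of 15 bpm or more.

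**Precedence.** SAP section 1 lets the SAP prevail over the protocol where they differ. SAP section 9 declares no changes from the protocol.

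**The concern.** The 1-h and 3-h readings after Dose 1 are the only post-dose vital signs in the trial with a fixed time from dosing. All later ones are taken at visits without a set interval. The protocol's dose rationale (7.4) treats heart-rate increase as related to peak concentration, so these are the readings best placed to describe it. They also support a randomised first-dose comparison: 300 mg in Group 1, 450 mg in Groups 2 to 4, and no omadacycline in Group 5.

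The protocol asks for them to be shown at the time they were measured. A rule that keeps one value per day, chosen by nearness to the dose, works against that, and because the SAP prevails the protocol wording does not clearly restore them. Separately, Table 11 has a change-from-baseline column which, as the CN sentence is written, appears to have no function.

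**Working it through.** **Step 1. Which Day 1 reading does the rule select?** The inputs are the windows in Protocol 8.5 and Schedule of Events note j. Distance is measured from the dose.

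| Reading | Distance from dose |
|---|---|
| Pre-dose | 0 to 30 min |
| 1 h | 60 − 15 = 45 min at least |
| 3 h | 180 − 15 = 165 min at least |

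The post-dose times run from completion of the dose, so their distance from its start is if anything longer.

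- *Reading A (literal).* Day 1 is an on-treatment day in Table 4 and all three readings compete. Since 30 < 45 < 165, an on-time pre-dose reading is always selected. By Table 2 it is also the baseline, so Day 1 change = pre-dose − pre-dose = 0. Both post-dose readings leave the by-visit summary.
- *Reading B.* The pre-dose value belongs only to the Baseline row of Table 4. The 1-h and 3-h readings compete. The 1-h window ends at 75 min and the 3-h window starts at 165 min, so the 1-h reading is selected and the 3-h reading leaves the by-visit summary.

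The rule returns one value per day, so neither reading keeps both post-dose values.

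**Step 2. Does SAP 8.6 restore them?** It summarises vital signs by time point. But 5.1.3 uses that term for a visit (its example is PTE), so the phrase does not clearly bring back readings within a day. The line graphs in 8.6 do not say which Day 1 values they plot.

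**Step 3. Where do the post-dose readings survive?** They enter the minimum and maximum post-baseline summaries, which include change from baseline and draw on all assessments. They also appear in the listings and, if the criterion value is met, in the overall post-baseline CN incidence. The maximum pools them with Day 3, Day 5, EOT and PTE readings, so a post-dose effect cannot be told from a rise at another visit.

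**Step 4. The CN rule.** Let A be the criterion value met and B the change criterion met. The rule is A or (A and B).

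| A | B | A or (A and B) |
|---|---|---|
| no | no | no |
| no | yes | no |
| yes | no | yes |
| yes | yes | yes |

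The result equals A in every row, so B never alters a flag.

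**Step 5. What the absolute limit means for heart rate.** Protocol 7.4 mentions rises of 12 to 17 bpm. Baseline needed to reach 120 bpm: 120 − 12 = 108, and 120 − 17 = 103. Rises from lower baselines are not flagged.

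**Step 6. Illustration only.** Baseline mean, baseline SD and SD of change are assumptions; the documents give none of them. Take baseline mean 75, baseline SD 10 to 12, SD of change 8 to 10, and a normal model.

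- P(change ≥ 15) = 1 − Φ((15 − d)/SD of change)
- P(heart rate ≥ 120) = 1 − Φ((120 − 75 − d)/√(baseline SD² + change SD²)), where the root runs from √(100 + 64) = 12.8 to √(144 + 100) = 15.6

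| Mean rise d | Rise ≥ 15 bpm | Heart rate ≥ 120 bpm |
|---|---|---|
| 17 bpm | 58–60% | 1.4–3.7% |
| 12 bpm | 35–38% | 0.5–1.7% |

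**The case against.** Several points on the other side are sound.

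- **Zero change is not certain.** Table 4 has a separate Baseline row that takes the last pre-dose value, and SAP 8.6 speaks of post-baseline values. Reading B is therefore reasonable, and under it Day 1 change is not zero. This stands, but reading B still loses the 3-h reading.
- **The rule may be only a tie-breaker.** SAP section 1 says the SAP is meant to agree with the protocol, and section 9 declares no change. The sentence could be aimed at surplus readings rather than scheduled ones. That may be the intent, but 5.1.3 makes no exception for scheduled readings.
- **The post-dose data do not vanish.** A reader might infer that a post-dose heart-rate rise would be absent from all output. The documents do not support that: the outputs in step 3 remain, and a systematic rise should shift the maximum-change summary relative to nitrofurantoin.
- **The redundancy hides no one.** A reader might infer that collapsing the CN rule to A is what loses moderate rises. It is not: A alone flags everyone that A and B together would flag, and neither limb flags on change alone. The defect is a column without effect.
- **The twice-daily arm is not singled out.** Groups 2, 3 and 4 take the same Dose 1, so these readings cannot separate Group 4 from Groups 2 and 3. The protocol's argument for that arm also concerns peak concentration at steady state, which Dose 1 does not represent.
- **The effect size is borrowed.** The 12 to 17 bpm rise comes from intravenous doses and is cited as "suggesting that heart rate increases above 12-17 bpm observed with 100-200mg IV doses in healthy patients is unlikely following 450mg twice daily dosing". Protocol 7.4 puts the oral peak at 1077 ng/mL against 2120 ng/mL for 100 mg IV, a ratio of 0.51. The percentages in step 6 are therefore not a forecast for this trial.

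**Conclusion.** Two limited defects stand.

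1. The same-day rule in SAP 5.1.3 conflicts with Protocol 12.6.1 for Day 1 heart rate and blood pressure. The by-visit summaries lose both scheduled post-dose readings under the literal rule (Day 1 change is then zero for every subject with an on-time pre-dose reading), or the 3-h reading if pre-dose values count as Baseline only. This assumes that time point in SAP 8.6 means visit, as it does in 5.1.3. The SAP does not settle which reading applies.
2. The CN rule in SAP 8.6 is logically the criterion value alone, so the change column of Table 11 has no effect. This needs no assumption.

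The consequence is a less informative descriptive safety display, not loss of the data or of every summary that contains them. The documents give no oral effect size or heart-rate variability from which to say how many subjects are affected. The correction is worth making because the readings are already collected and the protocol already promises the display.

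**What to change.** **SAP 5.1.3.** Exempt the protocol-scheduled Day 1 heart-rate and blood-pressure readings from the same-day rule. Tabulate pre-dose, 1 h and 3 h as separate time points by arm, with the change at 1 h and 3 h taken from the pre-dose value. The rule can stay for surplus readings on other days. State in SAP 8.6 that time point includes these readings, and that the line graphs plot them. This brings the SAP into line with Protocol 12.6.1 on this point, so no entry for it is needed in section 9.

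**SAP 8.6.** Make the change column operative by reporting separately the subjects who meet the criterion value, those who meet the change criterion, and those who meet both, using the existing Table 11 thresholds.

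**Cost.** SAP wording and a few more table rows, with no new data. The amendment should be approved before database lock, as SAP 3.5 already requires. The change row will pick up some ordinary variation and regression to the mean, and the nitrofurantoin arm shows how much to expect without omadacycline.
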